### 1.2 Study Rationale

PBC is a chronic disease and without effective treatment it is often progressive, leading to cirrhosis and liver failure, resulting in liver transplantation or death (EASL 2017). This study is being conducted in order to determine the effect of setanaxib on biochemical response based on ALP and fatigue in patients with PBC, elevated liver stiffness, and intolerance or inadequate response to UDCA. Intolerance to UDCA is defined as patients unable to tolerate the full-labeled dose of UDCA in PBC (13-15 mg/kg) due to frequently reported gastrointestinal symptoms such as diarrhea and abdominal pain.

This study will assess the decrease in ALP with daily doses of 1200 mg and 1600 mg versus placebo, whereas the previous PBC setanaxib Phase 2 study (GSN000300) investigated daily doses of 400 mg and 800 mg versus placebo.

Since the initial study design, there has been a significant evolution in the management of patients with PBC. In particular, the use of second-line therapies such as OCA (Ocaliva) and fibrates (eg, bezafibrate) has expanded, and a significant proportion of patients who are intolerant or nonresponders to UDCA are able to receive dual or triple therapy (ie, UDCA plus OCA and/or a fibrate). As a consequence, there appears to have been a general reduction in the level of disease activity observed in patients being considered for enrolment in the study (allowing for patients on dual or triple therapy), as judged by lower levels of ALP. This has likely decreased the available study population and consequently the rate of enrolment of patients into the study.

Based on the observed low enrolment rate, Calliditas does not consider it feasible to complete the study in its current format within a reasonable timeframe. It is nevertheless acknowledged that there is preliminary evidence of beneficial effects of setanaxib on important clinical aspects of PBC, including ALP, fatigue and related social and cognitive manifestations (Invernizzi et al 2023). Despite the evolution in the therapeutic approach to PBC, there still remain significant unmet needs, in particular with respect to quality of life outcomes such as fatigue, as this is typically unaffected by existing therapies (Jones et al 2023).

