### 4.1 Inclusion Criteria

The following inclusion criteria must be met for a patient to be eligible for inclusion in the study:

- 1. Male or female patient aged  $\geq 18$  years, inclusive at the time of informed consent.
- 2. Willing and able to give written informed consent and to comply with the requirements of the study.
- 3. Definite or probable PBC diagnosis as demonstrated by the presence of ≥2 of the following 3 diagnostic factors:
  - a. Documented history of elevated ALP levels ≥1.67×ULN of the local reference range.
  - b. Documented history of positive AMA titer or positive PBC-specific antibodies (anti-GP210 or anti-SP100 or antibodies against the major M2 components [PDC-E2, 2-oxo-glutaric acid dehydrogenase complex]).
  - c. Historical liver biopsy consistent with PBC.
- 4. Serum ALP  $\geq$ 1.67×ULN at Screening.

One repeat blood sampling (with analysis by the central laboratory) can be performed at the discretion of the Investigator at Screening Visit 2 for patients who do not meet this inclusion criterion at Screening Visit 1. If this inclusion criterion is then met at Screening Visit 2, the patient may be eligible for the study.

5. Liver stiffness measured by transient elastography (FibroScan®) of ≥8.0 kPa and an interquartile range over median ratio (IQR/med) of ≤30% at Screening, are taken with the results expressed in kilopascals [kPa]).

One repeat liver stiffness measurement can be performed within the Screening Period at the discretion of the Investigator for patients who do not meet the inclusion criterion at the initial screening assessment. If the inclusion criterion is then met, the patient may be eligible for the study.

6. UDCA prescriptional dose use for the past 6 months (at a stable dose for >3 months prior to Screening) OR intolerant to UDCA (last dose of UDCA >3 months prior to Screening). Intolerance to UDCA is defined as patients unable to tolerate the full-labeled dose of UDCA in PBC (13-15 mg/kg) due to frequently reported gastrointestinal symptoms such as diarrhea and abdominal pain.

- 7. For patients receiving OCA, fenofibrate, or bezafibrate treatment for at least 6 months and stable dose for >3 months prior to Screening.
- 8. For patients intolerant to OCA, OCA must have been discontinued >3 months prior to Screening.

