12.3 Treatments

12.3.1 Medical and PBC Treatment History

Medical history conditions will be coded using Medical Dictionary for Regulatory Activities (MedDRA) version 24.0 or later. The number and percentage of subjects with each medical history term will be listed

Version Date: 27-June-2024

Sponsor: Calliditas Therapeutics Suisse SA Protocol No: GSN000350

and summarized by the MedDRA system organ class (SOC) and preferred term (PT) using the FAS. A listing for medical history will be presented for the FAS.

PBC treatment history will also be presented for the FAS with the following baseline disease characteristics summarized:

Analysis (Yes/No)	Comment		
Any Prior PBC Treatment prior to or at randomization	The number and percentage of subjects have at least one ongoing PBC record at randomization, or a record on the PBC Treatment History page of the CRF		
UDCA use prior to or at randomization	Yes, if subjects have an ongoing UDCA record at randomization or a record for UDCA on the PBC Treatment History page of the CRF		
OCA use prior to or at randomization	Yes, if subjects have an ongoing OCA record at randomization or a record for OCA on the PBC Treatment History page of the CRF		
 Fibrate use (bezafibrate or fenofibrate) prior to or at randomization 	Yes, if subjects have an ongoing fibrate record at randomization or a record for OCA on the PBC Treatment History page of the CRF		
 Bezafibrate use prior to or at randomization 	Yes, if subjects have ongoing Bezafibrate record at randomization or a record for Bezafibrate on the PBC Treatment History page of the CRF		
 Fenofibrate use prior to or at randomization 	Yes, if subjects have ongoing Fenofibrate record at randomization or a record for Fenofibrate on the PBC Treatment History page of the CRF		
Any Prior PBC Treatment at randomization	The number and percentage of subjects have at least one ongoing PBC record at randomization.		
UDCA use at randomization	Yes, if subjects have an ongoing UDCA record at randomization		
OCA use at randomization	Yes, if subjects have ongoing OCA record at randomization		
 Fibrate use (bezafibrate or fenofibrate) at randomization 	Yes, if subjects have ongoing Fibrate record at randomization		
Bezafibrate use at randomization	Yes, if subjects have ongoing Bezafibrate record at randomization		
Fenofibrate use at randomization	Yes, if subjects have ongoing Fenofibrate record at randomization		

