Intolerance to UDCA	Yes, if a subject has a record on the PBC Treatment History page of the CRF with drug UDCA and reason for Reason Treatment was Discontinued is intolerance, otherwise if subject has an ongoing record for UDCA set to No		

All PBC treatment history will be listed for the FAS, Subjects who started PBC medication after randomization and subjects who stopped PBC medication prior to stopping randomized treatment will be flagged and a further flag if they were assessed to impact efficacy. Time to medication use will be derived and included in the listing.

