12.5.3.3 Supplementary Analyses

For the combined setanaxib treatment group versus placebo, where there is sufficient data (at least 10 patients at each level of the subgroup within each treatment group), additional *exploratory* analyses examining the consistency of the treatment difference among subgroups using the FAS will be performed. The primary analysis will be repeated at each level of the subgroup. A tabulation at Week 24 will be presented for each of the following subgroups:

- Age group: ≥18 and <65 years, ≥ 65 years
- Sex: Female vs Male
- Actual Randomization Strata: Screening serum ALP < or ≥3.0×ULN
- UDCA use ongoing at Randomization: Yes vs No
- UDCA use prior to or at Randomization: Yes vs No
- OCA use ongoing at Randomization: Yes vs No
- OCA use prior to or at Randomization: Yes vs No
- Fibrate use (bezafibrate or fenofibrate) ongoing at Randomization: Yes vs No

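### The SAP's fibrate-history row is triggered by an OCA record, so it miscounts past fibrate use, and one planned UDCA subgroup has no eligible patients at its No level

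*SAP*

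**What the plan says.** SAP 12.3.1 defines a table of PBC treatment history for the FAS, with one derivation rule per row. The combined fibrate row for use before or at randomization reads: "Yes, if subjects have an ongoing fibrate record at randomization or a record for OCA on the PBC Treatment History page of the CRF". The bezafibrate row beneath it reads: "Yes, if subjects have ongoing Bezafibrate record at randomization or a record for Bezafibrate on the PBC Treatment History page of the CRF". The fenofibrate row follows the same pattern with its own drug. A later row covers only current fibrate use: "Yes, if subjects have ongoing Fibrate record at randomization". The section also provides patient-level data: "All PBC treatment history will be listed for the FAS".

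SAP 12.5.3.3 plans exploratory subgroup analyses of combined setanaxib against placebo in the FAS. Each is run only where there are "at least 10 patients at each level of the subgroup within each treatment group". Five of the subgroups concern background PBC therapy: UDCA ongoing, UDCA ever, OCA ongoing, OCA ever, and fibrate ongoing. The second is "UDCA use prior to or at Randomization: Yes vs No".

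Protocol 4.1, inclusion criterion 6, admits patients who have used UDCA at a prescribed dose for the past 6 months, "OR intolerant to UDCA (last dose of UDCA >3 months prior to Screening"). Criteria 8 and 9 admit patients who stopped OCA because of intolerance, or stopped a fibrate, more than 3 months before Screening.

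**The concern.** The fibrate row's label and rule contradict each other. The OCA row just above carries the same history clause, which suggests a copying slip, but a programmer who follows the SAP will implement what is written. Criteria 8 and 9 admit exactly the patients who would be misclassified, so the category is not merely theoretical.

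The table has some weight. Randomization is stratified on Screening ALP only (SAP 8.2), and the primary model has no term for background therapy (SAP 12.5.2.1). Protocol 1.2 says that "a significant proportion of patients who are intolerant or nonresponders to UDCA are able to receive dual or triple therapy" and links the wider use of these drugs to lower ALP and slow enrolment. This table is therefore a main place to judge whether the arms are balanced on PBC treatment, and a wrong row could show an imbalance that does not exist or hide one that does.

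The subgroup list raises two related questions: whether every listed subgroup can have patients at both levels, and how often the size rule would let one run in a trial this small.

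**Working it through.** **1. The fibrate row.** Let F be an ongoing fibrate record, B a history record for bezafibrate or fenofibrate, and O a history record for OCA. The label means Yes = F or B. The rule as written gives Yes = F or O.

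| F | B | O | As labelled | As written | Result |
|---|---|---|---|---|---|
| yes | any | any | Yes | Yes | correct |
| no | yes | yes | Yes | Yes | correct, for the wrong reason |
| no | yes | no | Yes | No | past fibrate user missed |
| no | no | yes | No | Yes | never-fibrate patient counted |
| no | no | no | No | No | correct |

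Row count as written minus true count = (patients with O only) − (patients with past-only fibrate use and no O). The total can be too high or too low, or right by cancellation with individual patients still misclassified. The two drug-specific rows use the right drug, so the parent row can be larger than their union, or smaller than one of them. The documents do not say how many patients have either history, so the number affected cannot be computed.

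**2. Where the row is used.** The only fibrate subgroup in SAP 12.5.3.3 is by ongoing use, which has its own correct rule. The primary model in SAP 12.5.2.1 contains treatment, visit, log baseline ALP and their interactions, with no fibrate variable. No analysis set in SAP 9.6 refers to the row.

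**3. The UDCA-ever subgroup.** Criterion 6 has two routes. The first requires UDCA in the past 6 months. The second requires intolerance and a last UDCA dose, so UDCA was taken. Both give Yes. A No could arise only from an eligibility deviation or a missing record.

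**4. The size rule.** Plan figure first: 16 / (1 − 0.25) = 21.3, rounded up to 22 per arm, and 22 × 3 = 66. This matches SAP 8.1. Enrolling 60 to 70 at 1:1:1 gives about 20 to 24 placebo patients.

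With n patients in a group and X at one level, the rule needs 10 ≤ X ≤ n − 10:

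- 20 placebo: X = 10 only
- 22 placebo: X = 10 to 12 (45% to 55%)
- 23 placebo: X = 10 to 13
- 24 placebo: X = 10 to 14
- 44 combined setanaxib (total 66): X = 10 to 34

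The placebo group is the binding constraint. The documents give no share of patients on OCA, on fibrates or intolerant to UDCA, so the share p is an assumption. The chance that both groups qualify is the product of the two exact binomial probabilities, taking the groups as independent and all randomized patients as in the FAS:

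| Total (placebo / setanaxib) | p = 20% | 30% | 40% | 50% |
|---|---|---|---|---|
| 60 (20 / 40) | 0.05% | 2.5% | 12% | 18% |
| 66 (22 / 44) | 0.2% | 7.8% | 32% | 48% |
| 70 (23 / 47) | 0.4% | 11% | 41% | 60% |
| 70 (24 / 46) | 0.6% | 14% | 49% | 69% |

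**The case against.** The best defence is that this is one wrong drug name in one descriptive line. The rows for use at randomization are right, and current therapy is what bears most directly on ALP during the trial. Under criterion 7, ongoing OCA or fibrate must have been taken for at least 6 months, at a stable dose for more than 3, so its effect should largely be in baseline ALP, and the primary model analyses the ratio to baseline and adjusts for baseline. Past fibrate use can be recovered from the two drug-specific rows and the listing. All of this stands, and it limits the consequence. It does not make the row right: the rule contradicts its own label and will produce a wrong count if followed.

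The empty UDCA level is also harmless in practice, because the size rule would skip the subgroup and no misleading result would appear. That stands too; deleting it is tidying.

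On the size rule, a reader might infer that the background-therapy subgroups cannot meet it, and that this is certain with the design's 16 evaluable patients per arm, since 10 + 10 exceeds 16. The documents do not support that. SAP 12.5.3.3 uses the FAS, and SAP 9.6.3 requires only one post-baseline ALP value, so early dropouts count. Four of the five subgroups can qualify, with a chance of 48% at an even split and 66 enrolled, and 60% to 69% at 70. A minimum cell size is also a defensible guard for exploratory subgroup models, and keeping OCA and fibrates apart preserves drug-specific information. Nothing in the documents requires a single pooled second-line factor with an interaction model in place of the rule.

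**Conclusion.** The fibrate-history rule is wrong as written. It misclassifies patients with an OCA history record and no fibrate use, and patients with past-only fibrate use and no OCA history record. Its size in patients is unknown because the documents give no treatment-history frequencies. The UDCA-ever subgroup has an empty No level for every eligible patient.

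A reader might go further and infer that the trial misreports background therapy as a whole, or that the primary result is affected. Neither follows: the row feeds no model, subgroup or analysis set, and the other fibrate rows are correct. Nor is every past-only fibrate user miscoded, since one who also has an OCA history record is coded correctly. The documents associate second-line therapy with lower ALP but do not rank treatments by effect, so no claim about which matters most is available.

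As a note only, the ten-per-level rule needs a near-even placebo split. At 66 enrolled, the chance that a given subgroup runs is below 8% if the smaller level holds 30% of patients or fewer. Most background-therapy subgroups may therefore not be produced, but this depends on shares that the documents do not give.

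**What to change.** In SAP 12.3.1, in the history clause of the combined fibrate row, replace OCA with bezafibrate or fenofibrate, so that the row equals the union of its two component rows. In SAP 12.5.3.3, and in the matching entry of the secondary-analysis summary table in 12.5.3.4, delete the subgroup by UDCA use before or at randomization; the subgroup by ongoing UDCA use stays.

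The cost is SAP wording and one line of programming, on data already collected. There is no statistical downside. The size rule can stay. A sentence saying that it needs at least 20 placebo patients, split nearly evenly, would prepare readers for subgroups that are not run.

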12.3.2 Prior and Concomitant Medications

Prior Non-PBC medications, concomitant Non-PBC medications (by treatment periods) and concomitant PBC medications (by treatment periods) received with IMP, categorized by medication group according to the World Health Organization Drug Dictionary (WHODRUG) Global version March 2021 B3 or later will be summarized using the SS.

Version Date: 27-June-2024

Sponsor: Calliditas Therapeutics Suisse SA

Protocol No: GSN000350

Prior and concomitant medications will be summarized using Anatomic Therapeutic Chemical (ATC) classification and PT for the SS. Where multiple ATC codes are assigned to the same treatment, the blinded Calliditas medical monitor will identify the primary code for inclusion in the summary tables. The number and percentage of subjects using each medication will be displayed together with the number and percentage of subjects using at least one medication within each medication group and subgroup. The summaries will be repeated for each treatment period, as defined in Section 10.7.1.

All Non-PBC medications will be provided in listing and flags will be provided, to indicate prior or concomitant medications, and to indicate treatment periods.

During the blinded data review meeting that was conducted prior to database lock, it was identified that a small number of concomitant Non-PBC medications were included on the concomitant PBC medication eCRF form. A list of associated ATC codes were provided by the Calliditas medical monitor to the ICON programming group to facilitate a move of these medications to the correct summary table.

12.3.3 Extent of Study Drug Exposure

The extent of exposure will be characterized for the SS according to the number of subjects who received at least one dose, the total number of doses received, the duration of therapy (weeks), duration of interruptions, the reasons for interruptions and study drug compliance. The summaries will be repeated for each treatment period, as defined in Section 10.7.1.

At each dispensing visit, subjects will be dispensed kit(s) comprising of 4 bottles containing 70 tablets each. Subjects are expected to take 4 tablets per day, 1 tablet from each bottle, 2 in the morning, 2 tablets in the evening.

The duration of exposure, regardless of temporary interruptions, will be defined as the

$$Duration (weeks) = \frac{(Last dose of IMP - First dose of IMP) + 1}{7}$$

The date of last dose of IMP in the 24-week treatment period and date of last dose in the 52-week treatment period (for subjects who received more than 24 weeks of treatment), respectively will be used in the above derivation. For the Extension Phase, the date of last dose of IMP in the Extension Phase will be used in the extension phase will be used in the above derivation and this data will be listed only.

During the course of the study, the dose may be interrupted due to safety concerns. The start date and end date of the interruption will be recorded on the Dose Interruptions page of the CRF. The number of subjects with an interruption at any point of the study will be summarized and the duration of interruption will be calculated as:

$$Duration \ of \ Interruption \ (weeks) = \frac{(End \ Date \ of \ Interruption - Start \ Date \ of \ Interruption) + 1}{7}$$

The reasons for the interruption will also be presented. If a subject has multiple interruptions during the study period, all individual interruptions will be summed to determine the overall period of treatment interruption.

The total number of doses administered will be calculated using values from the Drug Accountability CRF form and will be defined as:

 $Total\ Number\ of\ Doses\ Administered = Sum\ of\ no\ of\ doses\ dispensed - Sum\ of\ no\ of\ doses\ returned$

With the doses dispensed at a visit calculated as the number of bottles dispensed at a visit multiplied by the amount of tablets per bottle dispensed (70 tablets per bottle). The number of doses returned at a visit will be the sum of all tablets returned per bottle. If at a visit the number of doses returned for a bottle is missing, it will be assumed that the subject used the full amount of tablets in a bottle i.e. 0 will be used as the returned amount in the calculation. The total number of doses administered will be summarized for the Main Part. Extension Phase and Overall.

The compliance to study drug will also be calculated as:

Sponsor: Calliditas Therapeutics Suisse SA

Protocol No: GSN000350

 $Compliance~(\%) = 100* \frac{Total~Number~of~Doses~Administered}{Expected~number~of~tablets~to~be~taken}$

The expected number of tablets to be taken will be estimated based on the duration of exposure and defined as:

(Date of last dose in the period of interest – date of first dose in the study +1) X 4 tablets/day

The following compliance categories will also be displayed: <75%, ≥75 to <90%, ≥90%, 100%. Compliance and total number of doses administered will be calculated for the SS (by treatment period defined in Section 10.7.1) and Extension Phase (where applicable), where expected number of tablets will be the expected number during each reporting phase and total number of doses administered the number administered during each phase.

Study drug accountability, study drug compliance and interruptions will be listed.

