#### 6.4 Dose and Administration

Patients will be assigned to IMP as described in Section 6.3.

At each dispensing visit (Table 1), patients will receive kit(s) comprising 4 bottles (see Table 2). Each bottle contains 70 film-coated tablets. Patients will be dispensed 1 or

2 IMP kits at dispensing visits, as described in the site operations manual, to ensure that the patient has sufficient IMP to last until the next scheduled visit.

IMP	Bottles for mor	ning dosing	Bottles for evening dosing	
	Bottle 1	Bottle 2	Bottle 3	Bottle 4
Setanaxib 1200 mg/day	Setanaxib	Setanaxib	Setanaxib	Placebo
	400 mg tablets	400 mg tablets	400 mg tablets	tablets
Setanaxib 1600 mg/day	Setanaxib	Setanaxib	Setanaxib	Setanaxib
	400 mg tablets	400 mg tablets	400 mg tablets	400 mg tablets
Placebo	Placebo	Placebo	Placebo	Placebo
	tablets	tablets	tablets	tablets

Table 2Investigational Medicinal Product Kits

Patients will take 4 tablets per day, 1 tablet from each bottle. Two tablets will be taken in the morning and 2 tablets will be taken in the evening (see Table 2), for 24 weeks.

- Patients allocated to setanaxib 1200 mg/day will self-administer 2 tablets of setanaxib 400 mg in the morning, 1 tablet of setanaxib 400 mg in the evening, and 1 tablet of placebo in the evening.
- Patients allocated to setanaxib 1600 mg/day will self-administer 2 tablets of setanaxib 400 mg in the morning and 2 tablets of setanaxib 400 mg in the evening.
- Patients allocated to placebo will self-administer 2 placebo tablets in the morning and 2 placebo tablets in the evening.

Patients will be instructed not to take their morning IMP dose on visit days until after the study assessments have been completed.

The tablets should be taken orally with food or up to 30 minutes after eating a meal. Each tablet should be taken separately and swallowed whole with water. The patients will be instructed to distribute their morning and evening doses as even as possible.

For BID administration, the dosage interval should be at least 4 hours. A missed morning dose can therefore be taken up until 4 hours prior to the evening dose. Patients will be provided with a patient IMP dosing card. Patients will be instructed to record the date and time of each tablet that they take on the dosing card straight after they have taken the tablet.

Patients will be reminded to bring the IMP (including any empty bottles and packaging) and the patient IMP dosing card with them to each study visit.

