9.6.4 Per Protocol Analysis Set

Per Protocol analysis set (PPS) comprises of all subjects in the FAS who do not have any important protocol deviations during the 24-week treatment period that would potentially affect the efficacy of the study drug. Subjects will be analyzed based on the treatment group they were randomized to regardless of the actual treatment received.

Important protocol deviations are defined in the Protocol Deviation Guidance Document for the study. Prior to database lock and unblinding of the study, a blinded data review of the important protocol deviations (including programmatically determined deviations) will be performed to identify the important deviations impacting on the efficacy endpoints. This analysis set will be defined in a blinded manner prior to unblinding the study and agreed with Sponsor.

Deviations impacting efficacy that may lead to exclusion from the PPS will include:

- Deviations related to inclusion/exclusion criteria
- Incorrect treatment received (i.e. the actual treatment received is different to the initially randomized treatment at any point during the first 24-weeks of treatment)
- Non-compliance with study drug intake (≤80%) during the first 24-weeks of treatment
- Efficacy assessments at Week 24 performed significantly out of the protocol specified window
- Missing baseline data for the primary endpoint
- Use of prohibited concomitant medication that could have impacted the efficacy of study treatment.

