12.4 Important Protocol Deviations

Per ICON processes, protocol deviations data will be entered into the ICON system of record (PSO), in accordance with the Protocol Deviation Guidance Document. Important protocol deviations are defined in the protocol deviation guidance document. The final approved version of protocol deviation guidance will be finalized before the database lock for the primary analysis. The study team and the Sponsor will conduct on-going reviews of the deviation data from PSO, adjusting the deviation criteria as seems appropriate.

Protocol deviation data will be reviewed prior to database lock and important deviations with a potential impact on efficacy leading to the elimination of subjects from the PP will be identified. The PP must be finalized at the blinded data review meeting (or earlier), prior to database lock for the primary analysis and agreed with the Sponsor.

During the blinded data review meeting that was conducted prior to database lock, it was identified that several important deviations with impact on efficacy per section 9.6.4 were not entered into PSO. As such, programmatic PDs for deviations related to inclusion/exclusion criteria and non-compliance with study drug intake (≤80%) were derived and agreed in the blinded data review meeting and subsequently used as an additional protocol deviation source for analysis.

The number of subjects with important protocol deviations will be summarized in the FAS by category of violation and by treatment group including subset of Important protocol deviations leading to exclusion from the PP. For the primary analysis, all protocol deviations will also be listed. Deviations that occurred over a 24-weeks treatment period, over a 52-weeks treatment period and occurred during the extension phase will be flagged in the listings.

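### Scoring a missing tablet-return count as zero returned can push compliance above 100% and can lift a non-compliant patient over the 80% per-protocol cut

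*SAP*

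**What the plan says.** SAP 12.3.3 defines compliance as tablets administered divided by tablets expected. Administered is the sum dispensed minus the sum returned. Expected is the number of days from first to last dose in the period, times 4. For a missing return count, "it will be assumed that the subject used the full amount of tablets in a bottle", so zero is entered as the number returned. The section sets no cap at 100% and no handling for values above it, and its display categories stop at 100%.

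On supply, the SAP describes "kit(s) comprising of 4 bottles containing 70 tablets each" and adds that "Subjects are expected to take 4 tablets per day, 1 tablet from each bottle". Protocol 6.4 agrees ("Each bottle contains 70 film-coated tablets") and says that 1 or 2 kits are given at each dispensing visit, leaving the number to the site operations manual. Protocol Table 1 places dispensing at Baseline, Week 4 and Week 12.

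SAP 9.6.4 lists, among deviations that may lead to exclusion from the PPS, "Non-compliance with study drug intake (≤80%) during the first 24-weeks of treatment". SAP 12.4 reports that programmatic deviations for eligibility criteria and "non-compliance with study drug intake (≤80%) were derived and agreed in the blinded data review meeting", because several important deviations had not been entered in the deviation system. Neither section cites 12.3.3, but 12.3.3 holds the only compliance formula in the two documents.

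**The concern.** A zero for a missing return would be harmless if bottles were expected to come back empty. Here they are not. A patient who doses exactly as planned has tablets left at every dispensing visit, so for that patient the rule can err only upward, and it can give a value that is physically impossible.

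Two outputs are at stake. The total-dose and compliance summaries for the Safety Analysis Set would overstate intake wherever counts are missing. The 80% criterion could also pass a patient who should have been flagged. The PPS analysis is meant to show how far important deviations dilute the estimated effect (SAP 12.5.2.3). With about 16 evaluable patients per arm planned, a few wrongly retained non-compliers would weaken that check.

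**Working it through.** The documents state no compliance figure to reproduce, so the check applies the SAP 12.3.3 formula directly.

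**Inputs**
- Kit: 4 × 70 = 280 tablets, which is 70 days at 4 per day (SAP 12.3.3, Protocol 6.4).
- Intervals from Protocol Table 1: 28, 56 and 84 days, so 112, 224 and 336 tablets expected, 672 in total.
- Period: exposure and compliance are cut at Week 24, 168 days (SAP 10.7.1).
- Assumption: 1, 1 and 2 kits at Baseline, Week 4 and Week 12, the fewest that cover each interval from fresh supply. Kits are assumed to be used only in the interval for which they were dispensed.

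**Built-in leftovers under perfect dosing.** 280 − 112 = 168, 280 − 224 = 56 and 560 − 336 = 224 tablets.

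**Completer, no counts at all**
- 1+1+2 kits: 1120/672 = 166.7%.
- Fewest kits that can supply 672 tablets (three): 840/672 = 125.0%.
- Two kits at every visit: 1680/672 = 250.0%.

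**Early stopper, one kit, no counts**
- Last dose Day 28: 280/112 = 250%.
- Last dose Day 14: 280/56 = 500%.

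**Completer with 60% true intake, one whole interval uncounted (1+1+2 kits)**

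| Uncounted interval | Counted intake | Added by the rule | Score | Lowest true intake reaching 80% |
|---|---|---|---|---|
| Baseline to Week 4 | 0.6 × 560 = 336 | 280 | 616/672 = 91.7% | (537.6 − 280)/560 = 46% |
| Week 4 to 12 | 0.6 × 448 = 268.8 | 280 | 548.8/672 = 81.7% | (537.6 − 280)/448 = 57.5% |
| Week 12 to 24 | 0.6 × 336 = 201.6 | 560 | 761.6/672 = 113.3% | none: zero intake gives 560/672 = 83.3% |

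Here 537.6 = 0.8 × 672. A true 50% patient with the first interval uncounted scores (280 + 280)/672 = 83.3%.

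**Completer, one bottle uncounted.** The most it can add is 70/672 = 10.4 points. For a Baseline to Week 4 bottle, a true 75% patient scores (504 + 70 − 21)/672 = 82.3% and passes. A true 70% patient scores (470.4 + 70 − 19.6)/672 = 77.5% and is still flagged.

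**Counted intervals only.** The 60% patient with Week 12 to 24 uncounted scores 201.6/336 = 60.0%, against 113.3% under the present rule. This assumes even intake across intervals.

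**The case against.** The best defence is that the rule will rarely matter. It works bottle by bottle, and the large distortions need all the bottles of an interval to be uncounted. Protocol 6.9 requires returned tablets to be counted at each visit, entered in the eCRF and reconciled, and nothing in the documents suggests that whole kits often go uncounted. Meeting the 80% criterion does not exclude a patient automatically, because SAP 9.6.4 says only that it may. The deviation system and the blinded review are further routes to exclusion, and accountability and compliance are listed by patient. All of this stands, and it limits the consequence. It does not make the rule right, since the rule applies exactly where the count has failed.

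Three stronger readings are tempting.
- A reader might take 250% as the maximum. It is not a ceiling: earlier stoppers exceed it, and a completer on 1+1+2 kits cannot pass 167%.
- A reader might conclude that non-compliers are retained in the PPS. The documents show only that they can be, since the link from 12.3.3 to the criterion is inferred and other routes to exclusion exist.
- A reader might suppose that patients who do not return bottles are mostly poor compliers. That is plausible, but the documents give no support for it.

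**Conclusion.** The concern holds as a defect in a stated rule. Followed exactly, it gives impossible compliance: 167% for a completer with no counts on the assumed 1+1+2 kits, at least 125% under any scheme that covers 24 weeks, and more for early stoppers. It can carry a patient with 60% true intake past the 80% cut when a whole interval is uncounted, but a single missing bottle changes the classification only of a completer already within about 10 points of the cut.

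The reach is modest. Duration of exposure and interruptions are computed from dates and are unaffected; only total doses and compliance change. The PPS is touched only if the programmatic 80% deviation used the 12.3.3 formula. It is a supplementary analysis, and the FAS primary analysis does not depend on compliance. The kit numbers are an assumption, and how often counts are missing is not known from the documents.

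**What to change.** In SAP 12.3.3, replace the zero-return rule. Compute compliance only over dispensing intervals that have return counts, dropping an uncounted interval from both numerator and denominator. In SAP 9.6.4, state that the 80% criterion uses this value.

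Add a rule for the cases this leaves open. A patient with no usable counts has no compliance value, so would not meet the criterion and would pass unflagged by default. Send those patients, and any with a value above 100%, to blinded review for a PPS decision before unblinding.

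The cost is SAP wording and a small programming change. SAP 12.4 describes the blinded review as already held, so the affected patients may have to be taken back to it. The downside is that compliance will be unknown for some intervals or patients. Filling gaps from the dosing card is not part of this proposal: the card is a source document, but Protocol 6.4 requires eCRF entry only of the dose before PK visits, so using it more widely would probably need new data retrieval.
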